# 15. PROPOSED SAMPLE SIZE

#### Primary Hypothesis

To demonstrate the superiority of biomarker-led IS withdrawal over maintenance IS for hard clinical outcomes such as long term survival or incidence of IS-related side effects, the trial would require an unrealistically large sample size and a very lengthy follow-up. Notwithstanding, given the well known potential long-term benefits of IS withdrawal and the health-economic implications, the current study has been designed and powered to test the hypothesis that the IS weaning under the novel "Biomarker-based" strategy (Arm B+) is superior to Weaning All (Arm A), with respect to the proportion of participants who, having started the IS withdrawal protocol, complete it successfully without undergoing allograft rejection. Comparing arms A and B+ will show the utility of the biomarker as a clinical decision tool, as a function of its predictive accuracy. We have established that for the biomarker to drive safe IS withdrawal its Positive Predictive Value (*PPV* =  $\frac{Number Actually Tolerant}{Number Biomarker+}$ ) should be no less than 0.80, which would result into a statistically significant difference in the proportion of successfully weaned participants between arms A and B+. If the biomaker's PPV was 0.50, then participants in arm B+ would be no

better than taken at random, and there would be no difference with respect to arm A. Additionally, for the biomarker test to be considered successfully validated for clinical use, its sensitivity as estimated within arm A should be at least 0.70.

Expectations:

- **Biomarker Allocation:** Approximately 50% of participants will be positive for the biomarker (17).
- Arm A: 50% Successfully weaned participants vs.
- Arm B+: Under H0: 50% successfully weaned participants (if PPV = 0.50); under H1: 80% or more successfully weaned participants (if PPV ≥ 0.80).

100 participants would be sufficient to show superiority of Arm B+ compared to Arm A, with 90% power and 5% type I error rate, assuming an allocation ratio of 2:1 between arms A and B+ (given 50% biomarker positive). The resulting sample size including participants allocated to arm B- would be 134 subjects. To account for dropouts, the final sample size will be increased in 10%, resulting in a total of 148 participants.

# 16. STATISTICAL ANALYSIS

#### 16.1 Primary Analysis

To test for superiority of arm B+, compared to arm A, we will compare the proportion of successfully weaned participants in each arm using generalized linear mixed models (GLMM) (logistic regression) with random effects for study centre, as a factor used in the minimisation procedure. Potential confounding will be examined, as part of sensitivity analysis, for the following covariates: (study centre, age at randomization, time from transplantation at randomization, a binary indicator of whether the participant was receiving a second drug at baseline). The primary outcome will be analysed per Intention-to-Treat, i.e. participants allocated to arms A or B+ who do not start the weaning protocol or initiate weaning but do not complete it, will be treated as 'failures'. To ultimately validate the clinical utility of the biomarker, 2 further conditions will need to be met: 1) the confidence interval of the proportion of successes in arm B+ should include 0.80 and exclude 0.50; and 2) the confidence interval of the test's sensitivity as estimated in arm A should include 0.70 and exclude 0.50.

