### 5.2 Primary Objective:

To determine if the use of a liver tissue transcriptional test of tolerance to stratify liver recipients prior to IS withdrawal accurately identifies operationally tolerant recipients and reduces the incidence of rejection, as compared with a control group in whom IS withdrawal is performed without stratification.

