#### - Discontinuation of IS Weaning/Resumption of IS:

- Participants undergoing IS weaning who experience rejection will be re-started on IS and will not be allowed a second attempt.
- Participants who have successfully completed IS weaning and who subsequently experience rejection will be re-started on IS.
- Participants who cannot complete the IS weaning protocol and do not experience rejection will remain in the study but will be considered as 'failures'.

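### Section 16.1 judges the biomarker's PPV on a success proportion that scores never-weaned and non-graft stops in B+ as not tolerant, biasing it downwards by an amount that depends on early loss

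*Protocol*

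**What the plan says.** Protocol sections 5.4 and 15 define PPV as actually tolerant participants divided by biomarker-positive participants. Section 15 says that it "should be no less than 0.80, which would result into a statistically significant difference" between A and B+. The planning values are "50% Successfully weaned participants vs" (arm A) and, in B+, "80% or more successfully weaned participants (if PPV ≥ 0.80"). Section 15 words the hypothesis for participants who have begun withdrawal. It then inflates the evaluable number: "To account for dropouts, the final sample size will be increased in 10" per cent, from 134 to 148. Section 5.2 asks whether the test "accurately identifies operationally tolerant recipients".

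Section 16.1 analyses the primary outcome by intention to treat (ITT) and counts as failures those allocated to A or B+ "who do not start the weaning protocol or initiate weaning but do not complete it, will be treated as 'failures". Section 8.3 agrees: "Participants who cannot complete the IS weaning protocol and do not experience rejection will remain in the study but will be considered as 'failures". Section 12.1 defines failed withdrawal as non-completion whatever the cause. The next sentence of 16.1 sets the first validation condition: "the confidence interval of the proportion of successes in arm B+ should include 0.80 and exclude 0.50". No other PPV estimate is defined. Section 16.3 bases a stop/go decision at 33% on the PPV without saying how non-completers are counted.

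**The concern.** The reference standard for tolerance is an attempted withdrawal and its outcome. A B+ participant who withdraws consent before weaning, becomes pregnant, or is stopped for a medical reason unconnected with the graft has not had that standard applied. Scoring such people as failures turns the B+ proportion into the share of biomarker-positives who end up weaned when offered it. That differs from the share who are tolerant, which is what sections 5.4 and 15 define.

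For the A versus B+ contrast this is a sound choice, because both arms carry attrition under one rule. The validation condition compares a single proportion with fixed values of 0.80 and 0.50, so no comparator absorbs the added failures. At stake is a test that truly meets the 0.80 target being refused validation because of attrition rather than rejection.

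The two sections also handle the same people differently. Section 15 frames the hypothesis among those who started and treats dropouts as removed from the evaluable number. Section 16.1 keeps non-starters and non-completers in the denominator as failures.

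**Working it through.** **1. The plan's sample size.** Inputs from section 15: 0.50 in A, 0.80 in B+, 90% power, 5% type I error (two-sided reproduces the figure), A:B+ of 2:1. With unpooled variance:

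n_A = (1.960 + 1.282)² × (0.25 + 0.16/0.5) / 0.30² = 66.5, so 67, with 33 to 34 in B+, or 100 to 101 in all. Then 2 × 67 = 134, and 134 × 1.10 = 147.4, so 148.

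The plan's 100/134/148 is reproduced. In this chain the 0.80 applies to the participants who remain, and the 10% is lost from the count.

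**2. Size of B+.** 148/2 = 74 per arm. With half biomarker-positive (section 15), B+ has 37. A 10% loss leaves 37 × 0.90 ≈ 33.

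**3. Attenuation.** Let d be the fraction of B+ lost before weaning is complete, for non-graft reasons and independently of tolerance. The expected B+ proportion is PPV × (1 − d):

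- d = 5%: 0.80 × 0.95 = 0.76
- d = 10%: 0.80 × 0.90 = 0.72
- d = 15%: 0.80 × 0.85 = 0.68

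**4. Chance of meeting condition 1.** I applied the rule literally: the 95% confidence interval contains 0.80 and excludes 0.50. With n = 37, exact (Clopper-Pearson) and Wilson intervals accept the same outcomes, 25 to 34 successes. Binomial probabilities of that range:

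| Loss d | Expected proportion | Chance of meeting condition 1 |
|---|---|---|
| 0% | 0.80 | 96.3% |
| 5% | 0.76 | 91.1% |
| 10% | 0.72 | 78.6% |
| 15% | 0.68 | 59.9% |

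**5. Like-for-like comparison at 10% loss.** With the 33 observed participants and p = 0.80, the accepted range is 23 to 31 (exact) or 23 to 30 (Wilson), giving 94.3% or 92.2%. The part due to the scoring rule is 94.3 − 78.6 = 15.7 points, or 92.2 − 78.6 = 13.6 points. The remainder of the fall from 96.3% is the smaller sample, which attrition causes under either rule.

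**6. The 33% rule, if scored the same way.** Section 16.3 does not give the number of biomarker-positives at that look. I assume 12 (37/3 ≈ 12.3). The stop region is an interval that excludes 0.80 but not 0.50, which in the lower tail means 6 or fewer successes of 12 with either interval. Its probability is 1.9% at 0.80 and 8.9% at 0.72. With 24 assumed instead, it is 1.3% and 10.6% (exact), or 3.6% and 20.6% (Wilson).

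**7. Sensitivity.** In arm A this is the biomarker-positive share of the successes. If loss is unrelated to biomarker status, numerator and denominator both shrink by (1 − d) and the ratio is unchanged.

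**The case against.** The choice looks deliberate. Section 9.1 makes successful withdrawal the gold standard for validating the biomarker's usefulness, section 15 expresses the 0.80 on that scale, and section 16.1 presents the condition as one of clinical utility. Counting unverified people as failures is conservative and makes validating a weak test harder. An evaluable-only PPV carries its own risk: if people stopped for supposedly non-graft reasons are less often tolerant, it overstates the PPV of a test meant to make withdrawal safe. Evaluable sets are also often defined in the SAP, which is not shown.

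Much of this stands. It is why the ITT proportion should stay in view as the worst case. It does not remove the problem: section 9.1 does not say that a person never weaned counts as negative, and the protocol itself defines PPV by actual tolerance and then tests it on another quantity.

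Three stronger readings should be resisted.

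- A reader might infer that a true 0.80 will be estimated at 0.72. The 10% is an overall dropout allowance, whereas the 16.1 failure rule concerns only starting and completing weaning, which takes 6 to 12 of the 48 months (section 5.5). Section 10.3.3 starts weaning at the Randomisation Visit, which limits non-starters. If half the loss came after weaning, the figure would be 0.76. Participants who stop weaning but stay in the study could push it the other way.
- A reader might infer that validation would fail. It would not by itself: 27 of 37 (0.73, exact interval 0.56 to 0.86) still meets the condition.
- A reader might infer that section 16.3 imposes the failure rule on the interim PPV. It states no such rule. Even for condition 1, the link is inferred from the shared paragraph and the word for successes, though strongly.

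**Conclusion.** The point holds in a limited form. Condition 1 in section 16.1 tests the PPV target on a proportion in which some biomarker-positive people of unknown tolerance count as test errors, and this conflicts with the definition and denominator in section 15. The bias is downwards. Its size is not fixed by the protocol: nil with no early non-graft loss in B+, 0.04 at 5% and 0.08 at 10%. At 10%, the scoring rule costs about 14 to 16 percentage points in the chance of meeting the condition. These figures assume 37 in B+, 95% intervals, a true PPV of exactly 0.80 and loss unrelated to tolerance. The interim effect is conditional on the same scoring being used there and on an assumed number of biomarker-positives. The matter deserves correction because the remedy is cheap; it does not undermine the primary comparison or the sensitivity condition.

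**What to change.** Keep the ITT failure rule for the A versus B+ comparison. For condition 1 in section 16.1, and explicitly for the PPV in section 16.3, define the PPV estimate as follows:

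- Include biomarker-positive participants who started weaning and whose tolerance status was observed.
- Count rejection, allograft dysfunction, Table 4 or Table 5 histology, or restart of immunosuppression for a graft reason as non-tolerant.
- Leave out, or multiply impute, only those never weaned or stopped for a documented non-graft reason. Classify them blind to the biomarker result, from the reasons for failed withdrawal that section 9.2.1 already collects. Section 5.4 keeps weaned participants and their physicians blinded, so this is feasible.
- Report the ITT proportion beside it as the worst case.

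Align the hypothesis wording in section 15 with whichever denominator each analysis uses.

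The cost is wording, with no new data. The interval is slightly wider (about 33 rather than 37 at 10% loss), and the estimate assumes that non-graft stopping is unrelated to tolerance. The ITT figure shows how much rests on that assumption.

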In contrast, analyses of liver biopsies by microarray, followed by validation of gene changes by realtime PCR, identified a group of 10 genes (*TFRC, PEBP1, MIF, CDHR2, SOCS1, IFNG, HAMP, SLC5A12, DAB2, HMOX1*) whose differential expression was significantly associated with tolerance, independently from all clinical parameters associated with successful IS withdrawal. An unexpected observation was the over-representation of genes involved in iron metabolism (e.g. transferrin receptor 1 (*TFRC*), hepcidin (*HAMP*), macrophage inhibitory factor (MIF)). This was consistent with the finding that tolerant and non-tolerant recipients differred in hepcidin and ferritin serum levels, as well as in hepatocyte iron deposition (higher in liver recipients successfully weaned from IS) (17). The significant correlation between intra-hepatic gene expression, serum hepcidin and markers of iron status, provided an indirect validation of the gene expression results, and suggested for the first time that changes in iron metabolism could be involved in the regulation of alloimmune responses and in the establishement of tolerance.

A combination of 5 out of the 10 genes measured at baseline (i.e. before IS was discontinued) was extremely accurate at discriminating those liver recipients who could successfully withdraw IS from those who could not (17). This predictive signature contained the following 5 genes: *SOCS1, TFRC, PEBP1, MIF, CDHR2*, and predicted the outcome of IS withdrawal with AUC=0.85, SN=89%, SP=86%, PPV=80%, and NPV=92%. The signature was different from those reported from PBMCs or whole blood and was highly reproducible across the 3 participating clinical sites. Thus, the test was originally identified in the 48 liver transplant recipients enrolled in Barcelona, and validated in an independent cohort of 21 recipients from Brussels and Rome (17).

[figure not shown]

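### The validation conditions in section 16.1 require the confidence intervals to contain 0.80 and 0.70, so the minimum standards of sections 5.4 and 15 also act as ceilings

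*Protocol*

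**What the plan says.** Section 16.1 (Primary Analysis) tests arm B+ against arm A for superiority and then adds: "To ultimately validate the clinical utility of the biomarker, 2 further conditions will need to be met". The first condition is that "the confidence interval of the proportion of successes in arm B+ should include 0.80 and exclude 0.50". The second is that "the confidence interval of the test's sensitivity as estimated in arm A should include 0.70 and exclude 0.50".

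Section 15 (Primary Hypothesis) states the same targets as floors. The PPV "should be no less than 0.80, which would result into a statistically significant difference" between arms A and B+; the alternative hypothesis is "80% or more successfully weaned participants (if PPV ≥ 0.80"; and for sensitivity, "its sensitivity as estimated within arm A should be at least 0.70". Section 5.4 gives the same two minimum values.

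Section 4.1.1 reports two sets of performance figures. The original signature "predicted the outcome of IS withdrawal with AUC=0.85, SN=89%, SP=86%, PPV=80%, and NPV=92"%. After re-calibration on the set-up to be used in this trial, sensitivity was 72% and PPV 82%.

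**The concern.** A floor is met by any value at or above it. A condition that the interval must contain the floor is not: once the lower limit passes the target, the interval no longer contains it and the condition fails. Under section 16.1, then, a PPV or sensitivity estimate can be too high for validation, and a test with no errors could not be validated at all. I found nothing in the protocol that lets an interval lying wholly above the target count as success.

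This clause decides whether the biomarker is declared validated. If the result came out high, the investigators would have to report non-validation of a test that exceeded its standard, or reinterpret the criterion after seeing the data.

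**Working it through.** **Inputs from the protocol.** Section 15: arm A success "50% Successfully weaned participants vs" 80% in B+; half of participants biomarker-positive; 90% power, 5% type I error, 2:1 allocation; 100 participants in A and B+, 134 with B-, 148 with dropout.

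**Reproducing the plan's sample size.** Unpooled normal formula, two-sided 5%:

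n(A) = (1.96 + 1.2816)² × (0.5×0.5 + 0.8×0.2/0.5) / 0.30² = 66.5, so 67. n(B+) = 33.3. The total is 99.8, so 100. Then 2 × 67 = 134, and 134 × 1.10 = 147.4, so 148. The stated figures are reproduced.

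**Group sizes for the check.** B+ is one quarter of the total: about 33 (of 134) or 37 (of 148). Tolerant participants in arm A are half of 67 or 74: again about 33 or 37.

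**Assumptions.** A 95% level and Clopper-Pearson intervals. Section 16.1 gives neither; section 16.3 uses 95% at the interims.

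**Which counts pass as written** (lower limit above 0.50 and target inside the interval):

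| Condition | n | Passing counts | First count failing as too high | Its 95% CI |
|---|---|---|---|---|
| PPV, 0.80 | 33 | 23–31 | 32/33 | 0.842–0.999 |
| PPV, 0.80 | 37 | 25–34 | 35/37 | 0.82–0.99 |
| Sensitivity, 0.70 | 33 | 23–28 | 29/33 | 0.718–0.966 |
| Sensitivity, 0.70 | 37 | 25–31 | 32/37 | 0.71–0.95 |

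**Probability of passing each condition**, summing binomial probabilities over the passing counts at n = 33:

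- PPV condition: 0.943 at true PPV 0.80, 0.961 at 0.85, 0.856 at 0.90, 0.496 at 0.95, 0 at 1.00. The maximum is near 0.83.
- Sensitivity condition: 0.584 at true sensitivity 0.70, 0.767 at 0.80, 0.558 at 0.85, 0.294 at 0.89, 0.023 at 0.95. The maximum is near 0.78.

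**Probability that the sensitivity condition fails because the result is too high:**

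- True sensitivity 0.72 (re-calibrated): 2%–3%.
- True sensitivity 0.80: 18% at n = 33 and 22% at n = 37. This value follows from section 15's own expectations: PPV × share positive / share tolerant = 0.80 × 0.50 / 0.50 = 0.80.
- True sensitivity 0.89 (originally published): 58% at n = 30, 71% at n = 33, 78% at n = 37.

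**Joint probability of superiority plus both conditions.** Simulation with 37 biomarker-positive and 37 biomarker-negative participants in arm A and 37 in B+, no dropout, with a two-proportion z-test standing in for the mixed model. The success rate among arm A negatives is set to PPV × (1 − sensitivity) / sensitivity, so that PPV and sensitivity take the stated values. The one-directional rule requires the lower limit above 0.50 and the upper limit at or above the target.

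| True PPV / sensitivity | As written | One-directional |
|---|---|---|
| 0.82 / 0.72 (re-calibrated) | 69% | 72% |
| 0.80 / 0.80 (implied by section 15) | 74% | about 89% |
| 0.80 / 0.89 (originally published) | 25% | 96% |
| 0.90 / 0.90 (illustrative) | 9% | over 99% |

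Wilson intervals give the same passing counts at n = 37. At n = 33, Wilson and Wald are as severe or more so: at true PPV 0.95 the PPV condition passes with probability 0.227 and 0.081, against 0.496 with exact intervals.

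**The case against.** The best defence is that the intention is plain. Sections 5.4 and 15 state floors, so a reader would take the condition to mean that the interval must be compatible with at least 0.80 or 0.70. That is probably what was meant, but section 16.1 does not say it, and its wording is definite enough that an SAP reading it otherwise would depart from the protocol. The missing interval level and method are a different matter: an SAP may supply them, and their absence is not counted as an error here.

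Three stronger readings are tempting, and the document does not support them.

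- *The trial's own assay is likely to be rejected for being too good.* The assay was re-calibrated on the trial set-up, with sensitivity 0.72 and PPV 0.82. There the ceiling costs about 3 percentage points. The large losses need a sensitivity near the originally published 0.89, or the illustrative 0.90/0.90, whose values exceed every figure the protocol reports for either measure.
- *A better test is always less likely to be validated.* The chance of passing rises up to and somewhat beyond the targets. At n = 33 it falls only beyond about PPV 0.83 and sensitivity 0.78.
- *Mediocre tests will be validated.* The PPV condition alone does accept 25/37 (68%, CI 0.502–0.820), and a true PPV of 0.65 meets it about 44% of the time. But it is added to the superiority test and the sensitivity condition; with all three, a test at 0.65/0.65 succeeds in about 10% of trials. Asking that an interval exclude 0.50 and remain compatible with 0.80 is a recognisable small-sample criterion.

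The interim in section 16.3 does not share the problem. Stopping there also requires no significant difference from 50%, so a very accurate test would not be stopped.

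**Conclusion.** The two conditions in section 16.1 are wrong as written, because they contradict the floors in sections 5.4 and 15 by failing a test whose interval lies wholly above its standard. The contradiction is in the text and does not depend on any calculation; only its size does. The loss is about 3 percentage points at the re-calibrated performance, about 15 at the values implied by section 15, and about 71 if sensitivity is really 0.89 with PPV 0.80.

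These sizes assume exact 95% intervals, about 33 to 37 participants in each denominator, no dropout in the joint figures, and a z-test in place of the mixed model. The primary superiority comparison and data collection are unaffected. The clause still deserves correction before results are known, because it governs the headline conclusion about the biomarker.

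**What to change.** Reword the two conditions in section 16.1 so that each works in one direction:

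- Success proportion in B+: the lower 95% limit is above 0.50 and the upper limit is not below 0.80.
- Sensitivity in arm A: the lower 95% limit is above 0.50 and the upper limit is not below 0.70.

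Add that an interval lying wholly above the target meets the condition, and state the level and interval method. The cost is two sentences in an amendment, with no extra patients or data.

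This removes the ceiling and nothing else: 25/37 would still meet the PPV condition. If the sponsor wants the section 15 minimum to hold for the estimate itself, the upper-limit clause can be replaced by a point estimate of at least 0.80 or 0.70. That is a stricter, optional choice with a real price: at 0.80/0.80 the joint probability of success would be about 52%, against about 89% under the one-directional interval rule.

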## 16.3 Interim analyses and stop/go decisions

We will carry out interim analyses when 33% and 50% of participants reach the primary outcome. At 33% we will calculate the 95% confidence interval of the PPV of the test that included the expected 80% PPV, and excluded a PPV of 50% with 90% power. Were the CI to exclude 80%, and show not to be significantly different from 50%, the trial will stop due to poor accuracy of the biomarker test. At 50% we will validate the sensitivity of the test using data from the 37 participants randomized to arm A only (weaning all), which will allow us to estimate with 80% power the 95% confidence interval of the sensitivity that included 70% and excluded 50%.

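### The validation rule in 16.1 requires the intervals to contain 0.80 and 0.70, so an interval lying wholly above either minimum fails

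*Protocol*

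**What the plan says.** Section 15 states both targets as floors. The PPV "should be no less than 0.80, which would result into a statistically significant difference", the alternative hypothesis for Arm B+ is a success rate of 80% or higher, and for clinical validation "its sensitivity as estimated within arm A should be at least 0.70". Section 5.4 gives the same two minima.

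Section 16.1 states the decision rule that applies after the superiority test of B+ against A: "To ultimately validate the clinical utility of the biomarker, 2 further conditions will need to be met". The first is that "the confidence interval of the proportion of successes in arm B+ should include 0.80 and exclude 0.50". The second is that "the confidence interval of the test's sensitivity as estimated in arm A should include 0.70 and exclude 0.50". No confidence level is given there, and no sentence says that an interval above the target also counts.

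Section 16.3 uses similar wording for sensitivity at the 50% look, where the aim is to estimate "the 95% confidence interval of the sensitivity that included 70% and excluded 50" per cent. Its PPV stopping rule at the 33% look is different: it stops the trial only if the interval excludes 80% and is also not significantly different from 50%.

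**The concern.** A floor is met by anything at or above it. A requirement that an interval contain the floor value is two-sided: it fails when the interval lies wholly below the value and also when it lies wholly above. Section 16.1 therefore puts a ceiling on each accuracy measure that sections 5.4 and 15 do not intend.

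These conditions decide whether the biomarker is declared validated. If the test did very well, the trial would have to report a validation failure, or else reinterpret a pre-specified success criterion after seeing the data. Neither is a good position, and both can be avoided now.

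**Working it through.** **Sample size, to fix the denominators.** Inputs from section 15: 50% v 80%, 5% type I error (taken as two-sided), 90% power, A:B+ = 2:1. Unpooled two-proportion formula:

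n(A) = (1.960 + 1.282)² × [0.5×0.5 + (0.8×0.2)/0.5] / 0.3² = 10.507 × 0.57 / 0.09 = 66.5, rounded to 67.

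B+ is then about 33, giving 100 in the comparison. With B−, 2 × 67 = 134, and 134 × 1.10 = 147.4, rounded to 148. The plan's figures reproduce and are not in dispute.

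**Denominators.** With half of participants biomarker-positive, B+ has about 67/2 ≈ 33 (from 134) to 74/2 = 37 (from 148). With half of Arm A tolerant, the sensitivity denominator is also about 33 to 37.

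**Assumptions.** 95% two-sided Clopper-Pearson intervals (the level is stated only in 16.3) and simple binomial counts without centre effects.

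**Counts that pass 16.1 as written.**

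| Condition | n | Passing counts | First count failing high | Its 95% CI |
|---|---|---|---|---|
| PPV, contain 0.80 | 33 | 23–31 | 32 (97%) | 0.842–0.999 |
| PPV, contain 0.80 | 37 | 25–34 | 35 (95%) | 0.818–0.993 |
| Sensitivity, contain 0.70 | 33 | 23–28 | 29 (88%) | 0.718–0.966 |
| Sensitivity, contain 0.70 | 37 | 25–31 | 32 (86%) | 0.712–0.955 |

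A perfect 37/37 in B+ (lower limit 0.905) fails.

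**Sensitivity implied by the plan.** Sensitivity = PPV × P(positive) / P(tolerant) = 0.80 × 0.50 / 0.50 = 0.80.

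**Probability of failing high (binomial, n = 33 to 37).**

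| True value | PPV condition | Sensitivity condition |
|---|---|---|
| Plan's expectations: PPV 0.80, sensitivity 0.80 | 0.6–1.3% | 18–22% |
| Re-calibrated test: PPV 0.82, sensitivity 0.72 | 1.2–2.7% | 2.6–3.1% |
| Original signature: PPV 0.80, sensitivity 0.89 | 0.6–1.3% | 71–78% |

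**Both conditions together.** They come from different arms, so the probabilities are multiplied.

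- Plan's expectations: 0.943 × 0.767 = 0.72 (n = 33) and 0.963 × 0.754 = 0.73 (n = 37). Without the ceiling: 0.949² = 0.90 and 0.977² = 0.95.
- Re-calibrated test, chance that at least one interval lies wholly above its target: 1 − (1 − 0.012)(1 − 0.026) = 3.8% (n = 33) and 1 − (1 − 0.027)(1 − 0.031) = 5.7% (n = 37).
- Original signature: 0.21–0.28, against 0.95–0.98 without the ceiling.

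**Shape.** Taken singly, the chance of passing rises to a peak at a true PPV of about 0.81–0.83 and a true sensitivity of about 0.76–0.78, and falls after that. Under the 50%/50% expectations PPV and sensitivity are equal. The joint chance then peaks at about 0.78–0.79 and falls throughout above 0.80: 0.72–0.73 at 0.80, 0.45–0.54 at 0.85 and 0.12–0.20 at 0.90.

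**Interval method.** Wilson limits give the same cut-offs at n = 37, and at n = 33 differ only in failing 31/33 on PPV. Wald limits are stricter at the top. The conclusion does not depend on the method.

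**The case against.** **The test being trialled is not the one with 89% sensitivity.** Section 4.1.1 first reports "SN=89%, SP=86%, PPV=80%, and NPV=92" (per cent) for the signature, then re-calibrates the algorithm on the trial's own platform and gives sensitivity 72% and PPV 82%. A reader might infer from the 89% that the biomarker would usually fail for being too good. The documents do not support that as the expected case. At the re-calibrated values the ceiling is the minor way to fail: the sensitivity condition fails low 21–31% of the time. This stands, and it limits the size of the problem. It does not remove it, because the plan's own design expectations imply a sensitivity of 0.80.

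**The PPV ceiling may rarely bite.** Section 16.1 counts B+ participants who do not start or finish weaning as failures. If the 10% dropout allowance were all lost that way (an assumption), a true PPV of 0.90 would appear as 0.81 and fail high about 2% of the time at n = 37, against 27% with no such loss. This stands: sensitivity is where the rule does most harm.

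**The intent is obvious.** Sections 5.4 and 15 do make it plain, and a sympathetic reader would accept an interval above the target. But 16.1 uses the same construction for both measures, and a success criterion should not depend on sympathetic reading after the result is known. An analysis plan that followed 16.1 would inherit the fault, and one that departed from it would contradict the protocol.

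**The superiority comparison is untouched.** This is true. The B+ v A test, the participants and the data are unaffected.

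**Conclusion.** The point holds. Section 16.1 contradicts the minima in sections 5.4 and 15, and followed literally it denies validation to a biomarker shown to exceed them. At the plan's own expectations this lowers the chance of meeting both conditions from 90–95% to about 72–73%, almost wholly through sensitivity. At the re-calibrated performance the loss is about 4–6%. These figures assume 95% exact intervals, 33 to 37 per denominator, no centre effects and, for PPV, no loss to incomplete weaning.

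Two stronger readings should not be drawn. One is that a better test always has a lower chance of passing. Each condition's chance falls only beyond its peak, so between the floor and that peak a better test passes more often. Only the joint chance, under the 50%/50% expectations, falls throughout above 0.80. The other is that 16.3 shares the defect in full. Its PPV rule cannot stop a trial whose interval lies wholly above 80%, and its sensitivity sentence describes the precision expected and attaches no stated consequence.

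Whether the floor is strict enough against poor tests (25/37, 68%, passes the PPV condition) is a separate question that this point does not settle.

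**What to change.** In 16.1, reword each condition as: *the lower confidence limit must exceed 0.50 and the interval must not lie entirely below 0.80* (*0.70* for sensitivity). An interval wholly above the target then counts as met. With this wording the chance of passing rises steadily with accuracy: at n = 33 to 37 both conditions together pass 90–95% of the time at 0.80 and 99% or more at 0.85.

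State the confidence level in 16.1 at the same time. In 16.3, align only the sensitivity sentence and leave the PPV stopping rule as it is.

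The cost is one sentence in each section, in a protocol amendment made before the outcome data are examined. No participants, data or procedures change.
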